7.2.2. Summary Measure

The difference in treatment mean change from baseline for WOMAC subscales scores and CCI will be analysed. In addition, the absolute and change from baseline values of WOMAC subscales scores, CCI and CCI (Individual and Overall) will be summarized descriptively by treatment. These scores will be also be listed by each participant and treatment.

Refer to Section 14.6.3 for details on calculation of WOMAC subscales scores.

The number of participants who took rescue medication will be summarised by treatment. In addition, the total weekly dose, average weekly dose and average rescue medication use will be summarized. A listing of rescue medication will be produced.

7.2.3. Population of Interest

The efficacy analyses will be based on the Intent-to-Treat population, unless otherwise specified.

7.2.4. Strategy for Intercurrent (Post-Randomization) Events

Intercurrent Events:

1. Treatment Withdrawal (Participant discontinues the study treatment but continues to stay in the study)

No imputations will be carried out if there are missing data due to intercurrent events.

A hypothetical strategy will be used to estimate what the treatment effect would have been had the subject not experienced the intercurrent event. Data collected after the occurrence of the Intercurrent Event will therefore not be used in the analysis. Since the dosing interval in this study is 7 days, the date of occurrence of the treatment withdrawal intercurrent event will be defined as the date of the first missed dose of study treatment

i.e. date of last dose of study treatment + 7 days. WOMAC, **CC1** and PainDetect are measured pre-dose at each weekly visit, therefore assessments after the date of last dose of study treatment + 7 days will be considered as occurring after treatment withdrawal. Rescue Medication is assessed daily in the evening, therefore Rescue Medication on or after the date of last dose of study treatment + 7 days will be considered as occurring after treatment withdrawal.

7.2.5. Statistical Analyses / Methods

7.2.5.1. Statistical Methodology Specification

Endpoint / Variables

 WOMAC pain, stiffness and function subscales scores at Week 1,2,4,6,8 CC1
Model Specification

 A Bayesian repeated measures model will be used to fit the change from baseline from Week 1 to Week 8. The endpoints will be assumed to follow a multivariate (MVN) normal distribution to model all repeated measurements within the same participant. Markov-Chain-Monte-Carlo (MCMC) method in SAS will be used to estimate the posterior distributions of the endpoints. A linear model for Change from Baseline at each Week (visit) will be constructed to model the within-subject covariance structures. Terms fitted in the model will include: 
 Categorical: Week, Treatment (GSK3858279 and placebo), Treatment*Week Interaction, Baseline*Week Interaction Continuous: Baseline Repeated: Week The prior for the Variance Covariance Matrix will follow an Inverse Wishart Distribution. Set simulation size at a minimum of 10000 and 1000 burn-in iterations. The simulation size and number of burn-in iterations could be updated during the convergence check. The vague priors (normal (0, var=1e6)) will be used for the hyperparameters/all model parameters - Refer to Appendix 6 - Bayesian Repeated Measures Model (PROC MCMC) for additional information Refer to Appendix 3 for details on visit computation. Refer to Appendix 9 for additional information
Model Checking & Diagnostics

 Bayesian Analyses: Refer to the relevant documentation (Bayesian Statistics Best Practice at GSK – Clinical Trials using Bayesian Inference). Refer to Appendix 9
Model Results Presentation

 Medians and 95% credible intervals will be produced by treatment group and for the difference between treatment groups each of the endpoints

- The posterior distributions will be used to produce several probability statements:
- For WOMAC pain, stiffness and function subscales scores
 - $P[\text{True Difference (GSK3858279 - placebo)} < X]$ where values of X to be generated are 0, -0.6, -0.8 and -1.0
- For **CCI** **CCI** 
- For all tables/figures presenting results from a statistical model, a footnote including model, prior distributions, covariates and a very brief mention of intercurrent events will be added.
- For all TFLs presenting efficacy endpoints, a footnote to state a range of the score for the endpoint specifying which direction of change is an improvement.

Subgroup Analyses

- No subgroup analyses is planned for the study.

8. SAFETY ANALYSES

The safety analyses will be based on the Safety population, unless otherwise specified.

8.1. Adverse Events Analyses

The definition of an AE is detailed in Appendix 3 of the protocol (Section 10.3).

Analyses of AEs will include those events that are on-treatment (Section 14.4.1).

Adverse events analyses including the analysis of Adverse Events (AEs), Serious (SAEs) and other significant AEs will be based on GSK Core Data Standards.

Details of the planned displays are presented in [Appendix 11](#).

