4.1.1. Treatment Groups and Duration

The total duration of the study (from signing of the informed consent until final follow-up) for each participant will vary between cohorts (see Table 1). The screening period will be of a maximum of 28 days for all cohorts in Part A and a maximum of 42 days in Part B. Final follow-up visits will be scheduled to occur when approximately 5 half-lives of GSK3858279 have elapsed after dosing. Follow-up visits are scheduled earlier for the lowest dose group where PK parameters are expected to be below the lower limit of quantification (LLQ), and are extended by an additional 4 weeks for the top dose cohort where extended pharmacology may be observed (see Table 1 and Schedule of Activities [SoA, Section 1.3]).

In Part A, each participant will receive a single dose of study intervention (GSK3858279 or placebo), either IV or SC. The planned dosing schedule is described in Table 1, although dose levels are subject to change depending on emerging study data. The maximum dose (level) that may be administered in the study will be 10 mg/kg, both for IV and SC cohorts. See Section 4.4 for further details.

In Part B, each participant will receive SC injections weekly for 8 weeks.

Table 1 Dosing schedule and study duration

Part	Cohort	Dose of GSK3858279	Follow up (days post dosing)	Maximum study duration including screening (days)
Part A	Cohort 1 IV	Up to 0.1 mg/kg	84	112
	Cohort 2 IV	Up to 0.3 mg/kg	112	140
	Cohort 3 IV	Up to 1 mg/kg	112	140
	Cohort 4 IV	Up to 3 mg/kg	112	140
	Cohort 5 IV	Up to 10 mg/kg	140	168
Cohort 6 SC	Between 1 and 3	140	168	
	Colloit 6 SC	mg/kg (max 240 mg)		
Part B	Cohort 7 SC	240 mg	56 (Treatment)	182/183
			84(Follow Up)	

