8.6.1. Time Period and Frequency for Collecting AE and SAE Information

- All SAEs will be collected from the start of study intervention until the followup visit at the time points specified in the SoA (Section 1.3). However, any
 SAEs assessed as related to study participation (e.g., study intervention,
 protocol-mandated procedures, invasive tests, or change in existing therapy) or
 related to a GSK product will be recorded from the time a participant consents to
 participate in the study.
- All AEs will be collected from the dose of study intervention until the follow-up visit (Section 1.3).

- Medical occurrences that begin before the start of study intervention but after obtaining informed consent will be recorded on the Medical History/Current Medical Conditions section of the CRF (not the AE section).
- All SAEs will be recorded and reported to the sponsor or designee immediately and under no circumstance should this exceed 24 hours, as indicated in Appendix 3. The investigator will submit any updated SAE data to the sponsor within 24 hours of it being available.
- Investigators are not obligated to actively seek AEs or SAEs in former study participants. However, if the investigator learns of any SAE, including a death, at any time after a participant has been discharged from the study, and he/she considers the event to be reasonably related to the study intervention or study participation, the investigator must promptly notify the sponsor.

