5.2. Study Treatment Display Descriptors

In the Tables, Listings and Figures (TLF), treatment should be presented with placebo first, then in order of increasing dose by route of administration within each part.

Part A: Treatment group descriptions			
RandAll NG		Data displays for reporting	
Code	Description	Description	Order in TLF
A	0.1 mg/kg IV GSK3858279	0.1 mg/kg IV GSK3858279	2
B	0.3 mg/kg IV GSK3858279	0.3 mg/kg IV GSK3858279	3
C	1 mg/kg IV GSK3858279	1 mg/kg IV GSK3858279	4
D	3 mg/kg IV GSK3858279	3 mg/kg IV GSK3858279	5
E	10 mg/kg IV GSK3858279	10 mg/kg IV GSK3858279	6
F	SC GSK3858279	3 mg/kg SC GSK3858279	7
P	Placebo	Placebo	1

Part B: Treatment group descriptions			
RandAll NG		Data displays for reporting	
Code	Description	Description	Order in TLF
G	240 mg SC GSK3858279	240 mg SC GSK3858279	2
P	Placebo	Placebo	1

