14.4. Appendix 4: Study Phases and Treatment Emergent Adverse Events

14.4.1. Study Phases

Assessments and events will be classified according to the time of occurrence relative to the first dose.

Study Phase	Definition
Pre-Treatment	Date/time < Study Treatment Start Date/time
On-Treatment	Study Treatment Start Date \leq Date/time

Refer SOA in [Appendix 2](#) for details of follow-up for each Cohort and Part.

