14.4.2. Treatment Emergent Flag for Adverse Events

Flag	Definition
Treatment Emergent	If AE start date \geq Study Treatment Start Date

NOTES:

- Time of study treatment dosing and start/stop time of AEs should be considered, if collected.

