14.11.7. Safety Tables

14.11.7.1. Part A

No.	Population	IDSL / Example Shell	Title	Programming Notes	Deliverable
Adverse Events (AEs)					
2.01.	Safety	AE1CP	Part A: Summary of All Adverse Events by System Organ Class and Preferred Term		Part A SAC
2.02.	Safety	AE5A	Part A: Summary of All Adverse Events by System Organ Class and Preferred Term and Maximum Intensity		Part A SAC
2.03.	Safety	AE5A	Part A: Summary of All Drug-Related Adverse Events by System Organ Class and Preferred Term and Maximum Intensity		Part A SAC
2.04.	Safety	AE15	Part A: Summary of All Non-serious Adverse Events by System Organ Class and Preferred Term (Number of Subjects and Occurrences)		Part A SAC
Vital Signs					
2.05.	Safety	VS1	Part A: Summary of Change from Baseline in Vital Signs	Includes Baseline values.	Part A SAC
2.06.	Safety	VS7	Part A: Summary of Worst Case Vital Signs Results by PCI Criteria Post-Baseline Relative to Baseline	Include all assessments post-baseline	Part A SAC
Laboratory: Hematology					
2.07.	Safety	LB1	Part A: Summary of Hematology Changes from Baseline	Includes baseline values.	Part A SAC
2.08.	Safety	LB17	Part A: Summary of Worst Case Hematology Results by PCI Criteria Post-Baseline Relative to Baseline	Include all assessments post-baseline	Part A SAC
Laboratory: Chemistry					
2.09.	Safety	LB1	Part A: Summary of Chemistry Changes from Baseline	ICH E3	Part A SAC
2.10.	Safety	LB17	Part A: Summary of Worst Case Chemistry Results by PCI Criteria Post-Baseline Relative to Baseline	ICH E3 Include all assessments post-baseline	Part A SAC

No.	Population	IDSL / Example Shell	Title	Programming Notes	Deliverable
Laboratory: Urinalysis					
2.11.	Safety	UR1	Part A: Summary of Worst Case Urinalysis Results (Discrete or Character Values) Post-Baseline Relative to Baseline		Part A SAC
ECG					
2.12.	Safety	EG1	Part A: Summary of ECG Findings		Part A SAC
2.13.	Safety	EG10	Part A: Summary of Maximum QTc Values Post-Baseline Relative to Baseline by Category	Use QTcB and QTcF intervals	Part A SAC
2.14.	Safety	EG2	Part A: Summary of Change from Baseline in ECG Values by Visit	Use QTcB and QTcF intervals	Part A SAC
2.15.	Safety	EG11	Part A: Summary of Maximum Increase in QTc Values Post-Baseline Relative to Baseline by Category	Use QTcB and QTcF intervals	Part A SAC
Telemetry – Part A					
2.16.	Safety	EG1	Part A: Summary of Telemetry Findings		Part A SAC

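### Part A adverse event percentages are confounded with follow-up time: 84 days at the lowest IV dose, 140 days at the highest and for SC, with no time adjustment

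*SAP*

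**What the plan says.** SAP 8.1 defines which events enter the AE tables: "Analyses of AEs will include those events that are on-treatment (Section 14.4.1". SAP 14.4.1 defines the on-treatment phase only by its start ("Study Treatment Start Date \leq Date/time"), and the treatment-emergent flag in SAP 14.4.2 is open-ended in the same way ("If AE start date \geq Study Treatment Start Date").

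The window therefore closes when collection stops. Protocol 8.6.1: "All AEs will be collected from the dose of study intervention until the follow-up visit (Section 1.3". That visit differs by cohort. In Protocol 4.1.1, Table 1, the row for the lowest dose reads "Up to 0.1 mg/kg 84 112", meaning 84 days of follow-up and 112 days in total with screening. The 0.3, 1 and 3 mg/kg IV cohorts have 112 days of follow-up; 10 mg/kg IV and SC have 140. The difference is deliberate: the lowest dose is followed for less time because drug levels are expected to fall below quantification, and visits "are extended by an additional 4 weeks for the top dose cohort where extended pharmacology may be observed".

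Each cohort contributes six active and two placebo participants (Protocol 4.2). Under SAP 5.2, "treatment should be presented with placebo first, then in order of increasing dose by route of administration within each part", with placebo as one group (code P). SAP 14.5.2 summarises categorical data as counts and percentages. None of the listed Part A AE tables (SAP 14.11.7.1, Tables 2.01 to 2.04) is limited to a common window or expressed per person-time, and SAP 14.6.2 derives days of exposure for Part B only.

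**The concern.** Safety and tolerability of escalating doses is the primary objective of Part A. The AE tables put placebo first and the active groups in dose order, so readers will look along the row. Planned follow-up never falls as IV dose rises, and it is 1.67 times as long at 10 mg/kg as at 0.1 mg/kg. An event after Day 85 cannot appear in the lowest-dose column. An event after Day 113 can appear only at 10 mg/kg IV, in the SC cohort and in those cohorts' own placebo participants. Even an inert drug would be expected to show a higher crude percentage at the top IV dose than at the bottom one. It would also show a higher percentage for SC than for 3 mg/kg IV, although SAP 5.2 labels the SC group 3 mg/kg as well. Table 2.04 also counts occurrences. Under a constant rate these grow in proportion to time, by the same factor of 1.67 between the two end doses.

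**Working it through.** **The plan's own figures.** Protocol 9.2.1 gives a 95% interval of 0.04 to 0.58 for one event in six, from a Beta(2,6) posterior. Its 2.5% and 97.5% quantiles are 0.037 and 0.579, which agree. The total durations in Protocol Table 1 are follow-up plus 28 days of screening: 84 + 28 = 112, 112 + 28 = 140, 140 + 28 = 168. These also agree.

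**Observation time.** Mean placebo follow-up = (84 + 3×112 + 2×140)/6 = 116.7 days. Relative to placebo: 84/116.7 = 0.72, 112/116.7 = 0.96, 140/116.7 = 1.20. Top against bottom IV dose: 140/84 = 1.67.

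**Expected percentages with no drug effect.** The documents give no background AE rate, so the proportion with at least one AE by Day 84 (p84) is assumed, from 10% to 80%. With a constant rate, P(t) = 1 − (1 − p84)^(t/84). Placebo is the mean over its six cohorts, [P(84) + 3P(112) + 2P(140)]/6. The last two columns are in percentage points, with participants out of 6 in brackets.

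| p84 | 0.1 IV (84 d) | 0.3, 1, 3 IV (112 d) | 10 IV and SC (140 d) | Placebo | 10 IV minus 0.1 IV | 10 IV minus placebo |
|---|---|---|---|---|---|---|
| 10% | 10.0 | 13.1 | 16.1 | 13.6 | 6.1 (0.37) | 2.5 (0.15) |
| 30% | 30.0 | 37.8 | 44.8 | 38.9 | 14.8 (0.89) | 6.0 (0.36) |
| 50% | 50.0 | 60.3 | 68.5 | 61.3 | 18.5 (1.11) | 7.2 (0.43) |
| 80% | 80.0 | 88.3 | 93.2 | 88.5 | 13.2 (0.79) | 4.6 (0.28) |

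The largest 10 versus 0.1 mg/kg gap at any constant rate is 18.6 points. The 0.1 mg/kg group falls about 4 to 11 points below placebo. SC exceeds 3 mg/kg IV by 3.0, 7.0, 8.2 and 4.9 points in the four rows (the 140-day column minus the 112-day column).

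**If AEs cluster soon after the single dose.** Suppose 80% of the cumulative hazard to Day 84 falls in the first 28 days and the rest continues at its later, constant rate. Days 28 to 84 and days 84 to 140 are both 56 days long, so P(140) = 1 − (1 − p84)^1.2. At p84 = 30% this is 34.8%, and at 50% it is 56.5%: gaps of 4.8 and 6.5 points, or 0.3 to 0.4 of a participant.

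**Against sampling noise.** The five IV cohorts with six active participants each were simulated 200,000 times, with a constant rate, no drug effect and p84 from 20% to 60%. The 10 mg/kg group had more affected participants than the 0.1 mg/kg group in 54% to 65% of trials, against 36% to 39% with equal follow-up. A one-sided 5% Cochran-Armitage trend test, which the plan does not include and is used here only as a gauge, was positive in 11% to 15%, against about 5% with equal follow-up.

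**After the fix.** In a common 84-day window the expected percentages are equal in all groups under no drug effect, so every gap above becomes 0. Planned person-days for the full-period column headers are 6×84 = 504 (0.1 IV), 6×112 = 672 (each of 0.3, 1 and 3 IV), 6×140 = 840 (each of 10 IV and SC) and 12×116.7 = 1,400 (placebo).

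**The case against.** A reader might infer that unequal follow-up alone would produce a dose trend across Part A. The documents do not support that. The 0.3, 1 and 3 mg/kg IV cohorts all have 112 days, so follow-up creates no gradient among them; only the two end IV doses differ, and SC against IV is a comparison of routes. Nor is there a formal comparison to be misled: Protocol 9.1 and SAP 2.4 state no hypotheses for Part A, and Protocol 9.4.2 makes safety descriptive. With six per group, a bias of about one participant at most lies well inside the plan's own interval of 0.04 to 0.58 for one event in six. A constant rate over 140 days after a single dose probably overstates the gap. Escalation decisions use data through 15 days post dose (Protocol 6.7), which every cohort has. All of this stands and limits the size of the point. It does not remove it, because the descriptive columns are the primary safety evidence, and this bias has a direction while noise does not.

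A reader might also infer that the worst-case tables, such as "Part A: Summary of Worst Case Vital Signs Results by PCI Criteria Post-Baseline Relative to Baseline", should be cut to common time points, since they take extremes over unequal numbers of readings. Scheduled post-baseline laboratory visits do run from 9 at 0.1 mg/kg to 12 at 10 mg/kg and SC, and post-dose vital-sign readings from 17 to 20 for IV against 13 for SC. But change-from-baseline summaries are already planned for vital signs, haematology, chemistry and ECG (Tables 2.05, 2.07, 2.09 and 2.14), and these allow comparison at matched times. Cutting the worst-case tables would drop most infusion-day vital signs. Making the full-period AE table secondary would likewise play down the period for which the top-dose follow-up was extended. Neither step is justified in a first-in-human study.

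**Conclusion.** The concern holds in a limited form. The planned crude AE percentages mix dose with observation time at the two ends of the IV range and in 3 mg/kg IV against SC. The bias runs towards a dose or route effect. For 10 against 0.1 mg/kg it is about 6 to 18.5 points (0.4 to 1.1 of 6 participants) under a constant rate, and about 5 to 6.5 points if AEs cluster early. For 10 mg/kg against placebo it is about 2.5 to 7 points under a constant rate. These sizes rest on an assumed AE rate and timing, no drug effect and complete planned follow-up; the direction needs only that some AEs arise after Day 85. The table shells are not in the documents, so the absence of a time adjustment is read from the table titles, programming notes and display conventions. The staggered follow-up itself is explained and is not at fault. What is missing is a display that allows for it.

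**What to change.** In SAP 8.1 and Appendix 11, add a Part A AE summary restricted to the window common to all cohorts, from first dose to Day 85, beside Tables 2.01 to 2.04. In the full-period tables, show person-days of follow-up in each column header, using actual rather than planned days. Keep the full-period AE tables and the worst-case vital-sign, laboratory and QTc tables as planned, so that late events and extreme values stay visible.

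With the half-life of about 18 days in SAP 14.6.2, the common window spans 84/18 = 4.7 half-lives, close to the roughly five that Protocol 4.1.1 aims for. The cost is one or two extra tables from existing data. The common-window table omits late events, which remain in the full-period tables and listings. SAP 3.2 allows Part A to be delivered before Part B ends; if that has happened, the new table should be labelled post hoc.

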14.4.1.1. Study Phases for Concomitant Medication

Study Phase	Definition
Prior	If medication end date is not missing and is >7 days prior to first dose.
Concomitant	Any medication that is not a prior

NOTE: Refer to [Appendix 7](#): Reporting Standards for Missing Data for handling of missing and partial dates for concomitant medication. Use the rules in this table if concomitant medication date is completely missing

In addition, the following phase will also be calculated:

Study Phase	Definition
Prohibited Medication Phase	If medication has start date on or before Day 71 and is either ongoing or has end date on or after 7 days prior to first dose (Section 6.6 of the Protocol)

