Missing start day	
 • If study treatment start date is missing (i.e. participant did not start study treatment), then set start date = 1st of month. • Else if study treatment start date is not missing: 
 ○ If month and year of start date = month and year of study treatment start date then 
 ▪ If stop date contains a full date and stop date is earlier than study treatment start date then set start date= 1st of month. ▪ Else set start date = study treatment start date. ○ Else set start date = 1st of month. 		

Element	Reporting Detail		
	Missing start day and month	
 • If study treatment start date is missing (i.e. participant did not start study treatment), then set start date = January 1. • Else if study treatment start date is not missing: 
 ◦ If year of start date = year of study treatment start date then 
 ▪ If stop date contains a full date and stop date is earlier than study treatment start date then set start date = January 1. ▪ Else set start date = study treatment start date. ◦ Else set start date = January 1. 	
	Missing stop day	Last day of the month will be used.	
	Missing stop day and month	No Imputation	
	Completely missing start/end date	No imputation	
Concomitant Medications	
 • Partial dates for any concomitant medications recorded in the CRF will be imputed using the following convention: 	Missing start day	
 • If study treatment start date is missing (i.e. participant did not start study treatment), then set start date = 1st of month. • Else if study treatment start date is not missing: 
 ◦ If month and year of start date = month and year of study treatment start date then 
 ▪ If stop date contains a full date and stop date is earlier than study treatment start date then set start date= 1st of month. ▪ Else set start date = study treatment start date. ◦ Else set start date = 1st of month.

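### Minor: an adverse event with no start date at all meets neither the on-treatment nor the treatment-emergent definition, so as written it is left out of the AE summary tables

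*SAP*

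**What the plan says.** SAP 8.1 defines the AE analysis set by study phase: "Analyses of AEs will include those events that are on-treatment", with a cross-reference to 14.4.1. There, an event is on-treatment if "Study Treatment Start Date \leq Date/time" and pre-treatment if its date falls before that start. SAP 14.4.2 sets the treatment-emergent flag by a similar test: "If AE start date \geq Study Treatment Start Date". None of these definitions has a clause for a missing date.

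SAP 14.7.2.1 explains that AE dates are imputed so that events can be placed in study periods. It has rules for a start date missing the day, or the day and month. For AEs in the row "Completely missing start/end date", it imputes nothing.

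For medications, SAP 14.4.1.1 covers the undated case explicitly: "Use the rules in this table if concomitant medication date is completely missing". That table classes any medication not shown to be prior as concomitant.

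Protocol 8.6.1 sets the collection window: "All AEs will be collected from the dose of study intervention until the follow-up visit". Occurrences between consent and first dose go to the medical history pages instead. The exception is SAEs related to study participation or to a product of the sponsor, which are recorded from consent.

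**The concern.** The SAP slots events by comparing dates, and for one class of AE it supplies no date to compare. An event that the protocol's collection rules make almost certainly post-dose then falls outside the tables meant to count post-dose events.

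This also runs against the SAP's own practice in neighbouring cases. An undated medication defaults to concomitant. An AE dated only to the month or year of treatment start is moved to the treatment start date unless a full stop date is earlier. Only the fully undated AE loses its place.

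Safety and tolerability is a primary objective of both parts, and the AE tables are its main display. What is at stake is a possible undercount of a few events at most. Nothing suggests that it would differ between arms or change a decision.

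**Working it through.** The plan states no figure on this point, so the main check applies its rules to each pattern of missing AE start date for a dosed participant.

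1. **Day missing, month and year known.** If month and year match those of treatment start, the rule is "Else set start date = study treatment start date", unless a full stop date is earlier than treatment start, in which case the first of the month is used. In any other month, the first of that month is used. The event has a date and a phase.
2. **Day and month missing, year known.** In the year of treatment start, the date becomes treatment start unless a full stop date is earlier, in which case it is January 1. In any other year it is January 1. The event again has a date and a phase.
3. **Nothing known, not even the year.** No date is imputed, so neither the 14.4.1 comparisons nor the 14.4.2 comparison can be made. The event is not pre-treatment, not on-treatment and not treatment-emergent. Under 8.1 it is not in the AE summaries, and under 14.4.2 it is not in Table 2.37.

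The gap is therefore confined to case 3. Such an event should still appear in the listings of all AEs (Listing 14 for Part A, Listing 47 for Part B).

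The effect of one record on a reported percentage is at most one participant divided by the group size. It is zero if the participant has another dated occurrence of the same term. Group sizes come from Protocol 4.2: in Part A, 6 active per cohort and 12 placebo in total, shown as one placebo group under SAP 5.2; in Part B, 1:1 allocation of 20, 50 or 80.

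| Group | Calculation | Effect of one participant (percentage points) |
|---|---|---|
| Part A active cohort | 1/6 | 16.7 |
| Part A placebo group | 1/12 | 8.3 |
| Part B arm, 20 in total | 1/10 | 10.0 |
| Part B arm, 50 in total | 1/25 | 4.0 |
| Part B arm, 80 in total | 1/40 | 2.5 |

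These are the effects of a single miscounted participant, whatever the cause. They do not say how often the rule would bite. The documents give no expected number of undated AEs; zero or very few is an assumption.

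**The case against.** The best counter-argument is that the SAP is silent here and does not exclude anything. Section 8.1 does not contain the word only. The main tables are titled as summaries of all adverse events. Declining to impute a date is not an instruction to drop the event, and an undated AE fails the pre-treatment definition too. The footnote in SAP 14.3 treats participants as on treatment for the whole study, which suggests that inclusion was intended. The SAP also defers to company standards: Core Data Standards in 8.1, IDSL in 14.5.2 and the legacy dataset standards in 14.5.1. Any of these may hold a default. Finally, with frequent visits, diary cards, source data verification and database cleaning, an AE without even a year should hardly occur.

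Much of this stands as a limit on size. Rarity, cleaning and the listings are why the point is minor, and the unseen standards are a real uncertainty. It does not remove the gap. A sentence saying which events the analyses will include is naturally read as restrictive, and neither the table titles nor the footnote gives a rule for undated AEs. The SAP applies IDSL only where it does not state otherwise, and here it does state a rule. Cleaning is a stated precondition of the final analyses (SAP 3.2), but several Part B AE tables are also scheduled for Interim Analysis 3 (SAP 14.11.7.2), for which the SAP states no equivalent precondition. Listings do not correct a table's count.

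**Conclusion.** The concern holds, as a minor point. Taken as written, SAP 8.1, 14.4.1, 14.4.2 and 14.7.2.1 together leave a fully undated AE out of the summaries although Protocol 8.6.1 makes it almost always post-dose. The word almost is needed because of the related SAEs recorded from consent. The expected impact is very small.

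The conclusion rests on the literal SAP text. If the company standards already class undated AEs as on-treatment, the remaining defect is only that the SAP does not say so. Confidence is medium for that reason.

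**What to change.** In SAP 14.4.1 and 14.4.2, with a cross-reference from 14.7.2.1, state that an AE with a completely missing start date is classed as on-treatment and treatment-emergent unless either:

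- its recorded or imputed stop date is before first dose; or
- its stop date is known only by year, and that year is before the year of treatment start.

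The second condition is needed because for AEs in the row "Missing stop day and month" the SAP does not impute a stop date, so there would be no full date to compare. If Part A has already been reported, apply the rule to Part B.

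The cost is one sentence in two places, one cross-reference and one programming condition. The downside is that an occasional pre-dose event may be counted, which for a safety display is the conservative direction.
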